### 6.1 Serious Adverse Events

A *Serious Adverse Event (SAE)* is any untoward medical occurrence that at any dose:

- results in death
- is life-threatening (defined as an event in which the subject was at risk of death at the time of the event; it does not refer to an event which hypothetically might have caused death if it were more severe)
- requires inpatient hospitalization or causes prolongation of existing hospitalization (see **NOTE** below)
- results in persistent or significant disability/incapacity
- is a congenital anomaly/birth defect
- is an important medical event (defined as a medical event(s) that may not be immediately life-threatening or result in death or hospitalization but, based upon appropriate medical and scientific judgment, may jeopardize the subject or may require intervention [eg, medical,

surgical] to prevent one of the other serious outcomes listed in the definition above.) Examples of such events include, but are not limited to, intensive treatment in an emergency room or at home for allergic bronchospasm; blood dyscrasias or convulsions that do not result in hospitalization.) Potential drug induced liver injury (DILI) is also considered an important medical event. (See Section 6.6 for the definition of potential DILI.)

•

Suspected transmission of an infectious agent (eg, pathogenic or nonpathogenic) via the study drug is an SAE.

Although pregnancy, overdose, cancer, and potential drug induced liver injury (DILI) are not always serious by regulatory definition, these events must be handled as SAEs. (See Section 6.1.1 for reporting pregnancies).

Any component of a study endpoint that is considered related to study therapy (eg, death is an endpoint, if death occurred due to anaphylaxis, anaphylaxis must be reported) should be reported as SAE (see Section 6.1.1 for reporting details).

**NOTE:**

The following hospitalizations are not considered SAEs in BMS clinical studies:

- a visit to the emergency room or other hospital department < 24 hours, that does not result in admission (unless considered an important medical or life-threatening event)
- elective surgery, planned prior to signing consent
- admissions as per protocol for a planned medical/surgical procedure
- routine health assessment requiring admission for baseline/trending of health status (eg, routine colonoscopy)
- medical/surgical admission other than to remedy ill health and planned prior to entry into the study. Appropriate documentation is required in these cases
- admission encountered for another life circumstance that carries no bearing on health status and requires no medical/surgical intervention (eg, lack of housing, economic inadequacy, caregiver respite, family circumstances, administrative reason)
- Admission for administration of anticancer therapy in the absence of any other SAEs (applies to oncology protocols).

**6.1.1 Serious Adverse Event Collection and Reporting**

Sections 5.6.1 and 5.6.2 in the Investigator Brochure (IB) represent the Reference Safety Information to determine expectedness of serious adverse events for expedited reporting. Following the subject's written consent to participate in the study, all SAEs, whether related or not related to study drug, must be collected, including those thought to be associated with protocol-specified procedures. All SAEs must be collected that occur during the screening period and within 100 days of discontinuation of dosing. For subjects randomized/assigned to treatment and never treated with study drug, SAE information should be collected for 30 days from the date of randomization.

The investigator must report any SAE that occurs after these time periods and that is believed to be related to study drug or protocol-specified procedure.

An SAE report must be completed for any event where doubt exists regarding its seriousness.

If the investigator believes that an SAE is not related to study drug, but is potentially related to the conditions of the study (such as withdrawal of previous therapy or a complication of a study procedure), the relationship must be specified in the narrative section of the SAE Report Form.

SAEs, whether related or not related to study drug, and pregnancies must be reported to Sponsor or designee within 24 hours of awareness of the event. SAEs must be recorded on the SAE Report Form; pregnancies on a Pregnancy Surveillance Form (electronic or paper forms). The preferred method for SAE data reporting collection is through the eCRF. The paper SAE/pregnancy surveillance forms are only intended as a back-up option when the eCRF system is not functioning. In this case, the paper forms are to be transmitted via email or confirmed facsimile (fax) transmission to:

**SAE Email Address:** Refer to Contact Information list.

**SAE Facsimile Number:** Refer to Contact Information list.

For studies capturing SAEs through electronic data capture (EDC), electronic submission is the required method for reporting. In the event the electronic system is unavailable for transmission, paper forms must be used and submitted immediately. When paper forms are used, the original paper forms are to remain on site.

**SAE Telephone Contact** (required for SAE and pregnancy reporting): Refer to Contact Information list.

If only limited information is initially available, follow-up reports are required. (Note: Follow-up SAE reports must include the same investigator term(s) initially reported.)

If an ongoing SAE changes in its intensity or relationship to study drug or if new information becomes available, the SAE report must be updated and submitted within 24 hours to Sponsor or designee using the same procedure used for transmitting the initial SAE report.

All SAEs must be followed to resolution or stabilization.

BMS will be reporting adverse events to regulatory authorities and ethics committees according to local applicable laws including European Directive 2001/20/EC and FDA Code of Federal Regulations 21 CFR Parts 312 and 320. A SUSAR (Suspected, Unexpected Serious Adverse Reaction) is a subset of SAEs and will be reported to the appropriate regulatory authorities and investigators following local and global guidelines and requirements.

## **6.2 Nonserious Adverse Events**

A *nonserious adverse event* is an AE not classified as serious.

### **6.2.1 Nonserious Adverse Event Collection and Reporting**

The collection of nonserious AE information should begin at initiation of study drug. Nonserious AE information should also be collected from the start of a placebo lead-in period or other observational period intended to establish a baseline status for the subjects.

Nonserious AEs should be followed to resolution or stabilization, or reported as SAEs if they become serious (see [Section 6.1.1](#)). Follow-up is also required for nonserious AEs that cause interruption or discontinuation of study drug and for those present at the end of study treatment as appropriate. All identified nonserious AEs must be recorded and described on the nonserious AE page of the CRF (paper or electronic).

Completion of supplemental CRFs may be requested for AEs and/or laboratory abnormalities that are reported/identified during the course of the study.

All nonserious adverse events (not only those deemed to be treatment-related) should be collected continuously during the treatment period and for a minimum of 100 days following discontinuation of study treatment.

Every adverse event must be assessed by the investigator with regard to whether it is considered immune-mediated. For events which are potentially immune-mediated, additional information will be collected on the subject's case report form.

### **6.3 Laboratory Test Result Abnormalities**

The following laboratory test result abnormalities should be captured on the nonserious AE CRF page or SAE Report Form (electronic) as appropriate. Paper forms are only intended as a back-up option when the electronic system is not functioning.

- Any laboratory test result that is clinically significant or meets the definition of an SAE
- Any laboratory test result abnormality that required the subject to have study drug discontinued or interrupted
- Any laboratory test result abnormality that required the subject to receive specific corrective therapy.

It is expected that wherever possible, the clinical rather than laboratory term would be used by the reporting investigator (eg, anemia versus low hemoglobin value).

### **6.4 Pregnancy**

If, following initiation of the study drug, it is subsequently discovered that a study subject is pregnant or may have been pregnant at the time of study exposure, including during at least 5 half lives after product administration, the investigator must immediately notify the Sponsor or designee of this event and complete and forward a Pregnancy Surveillance Form to BMS Designee within 24 hours of awareness of the event and in accordance with SAE reporting procedures described in [Section 6.1.1](#).

In most cases, the study drug will be permanently discontinued in an appropriate manner (eg, dose tapering if necessary for subject safety). Please call the Sponsor or designee within 24 hours of awareness of the pregnancy.

The investigator must immediately notify the Sponsor or designee of this event and complete and forward a Pregnancy Surveillance Form to Sponsor or designee within 24 hours of awareness of the event and in accordance with SAE reporting procedures described in [Section 6.1.1](#).

Follow-up information regarding the course of the pregnancy, including perinatal and neonatal outcome and, where applicable, offspring information must be reported on the Pregnancy Surveillance Form.

Any pregnancy that occurs in a female partner of a male study participant should be reported to Sponsor or designee. In order for BMS to collect any pregnancy surveillance information from the female partner, the female partner must sign an informed consent form for disclosure of this information. Information on this pregnancy will be collected on the Pregnancy Surveillance Form.

## **6.5 Overdose**

All occurrences of overdose must be reported as SAEs (see [Section 6.1.1](#) for reporting details).

## **6.6 Potential Drug Induced Liver Injury (DILI)**

Wherever possible, timely confirmation of initial liver-related laboratory abnormalities should occur prior to the reporting of a potential DILI event. All occurrences of potential DILIs, meeting the defined criteria, must be reported as SAEs (see [Section 6.1.1](#) for reporting details).

Potential drug induced liver injury is defined as:

- AT (ALT or AST) elevation > 3 times upper limit of normal (ULN)
- 7) AND
- Total bilirubin > 2 times ULN, without initial findings of cholestasis (elevated serum alkaline phosphatase),
- 8) AND
- No other immediately apparent possible causes of AT elevation and hyperbilirubinemia, including, but not limited to, viral hepatitis, pre-existing chronic or acute liver disease, or the administration of other drug(s) known to be hepatotoxic.

## **6.7 Other Safety Considerations**

Any significant worsening noted during interim or final physical examinations, electrocardiogram, x-ray filming, any other potential safety assessment required or not required by protocol should also be recorded as a nonserious or serious AE, as appropriate, and reported accordingly.

### **6.7.1 Adverse Events of Interest**

Immune-mediated adverse events (IMAEs) are AEs consistent with an immune-mediated mechanism or immune-mediated component for which non-inflammatory etiologies (eg, infection or tumor progression) have been ruled out. IMAEs can include events with an alternate etiology

which were exacerbated by the induction of autoimmunity. Information supporting the assessment will be collected on the subject's case report form.

## **7 DATA MONITORING COMMITTEE AND OTHER EXTERNAL COMMITTEES**

### **7.1 Data Monitoring Committee**

An independent Data Monitoring Committee (DMC) will be utilized. A DMC will be established to provide oversight of safety and efficacy considerations in CA209648. Additionally, the DMC will provide advice to the sponsor regarding actions the committee deems necessary for the continuing protection of subjects enrolled in the study. The DMC will be charged with assessing such actions in light of an acceptable benefit/risk profile for nivolumab plus ipilimumab and nivolumab plus fluorouracil and cisplatin. The DMC will act in an advisory capacity to BMS and will monitor subject safety and evaluate the available efficacy data for the study. The oncology therapeutic area of BMS has primary responsibility for design and conduct of the study.

DMC will review the safety data from the study when approximately (dependent on the accrual speed) 45 subjects (about 5% of subjects) have been treated and followed for at least 4 weeks.

Details of the DMC responsibilities and procedures will be specified in the DMC charter.

### **7.2 Independent Review of Progression at the Time of Investigator-Assessed Progression**

At the time of investigator-assessed initial radiographic progression per RECIST 1.1 in any given subject, the site must request the blinded independent review of progression from the third party radiology vendor.

Tumor assessments for each subject should be submitted to the radiology vendor as they are performed on an ongoing basis. The blinded, independent radiologists will review all available tumor assessments for that given subject and determine if RECIST 1.1 criteria for progression have been met. The independent assessment of whether or not the given subject met RECIST 1.1 criteria for progression will be provided to the site. Subjects whose disease progression is not confirmed centrally will be required to continue tumor assessments (if clinically feasible) according to the protocol-specified schedule. Subsequent tumor assessments must be submitted to the third party radiology vendor for subsequent review and may be discontinued when the investigator and independent radiologists both assess the subject to have met RECIST 1.1 criteria for progression.

In addition, subjects receiving treatment beyond progression must continue tumor assessments until such treatment has been discontinued.

If clinically acceptable, subsequent therapy should begin only after RECIST 1.1 progression has been assessed by Blinded Independent Central Review. For subjects who start palliative local therapy or subsequent therapy without prior assessment of RECIST 1.1 progression by central review, the Investigator must continue tumor assessments (if clinically feasible) according to the protocol-specified schedule and submit them to the third-party radiology vendor. When RECIST 1.1 progression is assessed by the investigator (whether assessed before or after the start of palliative local therapy or subsequent therapy), the Blinded Independent Central Review must be

requested. Tumor assessments may be discontinued when the independent radiologist assesses the subject to have met RECIST 1.1 criteria for progression.

## 8 STATISTICAL CONSIDERATIONS

### 8.1 Sample Size Determination

It is now established that time-to-events endpoints in I-O clinical trials tend to display specific characteristics. First, there may be long-term survival benefits in patients treated with immunotherapy - observed as a long lasting plateau towards the tail of the survival curve (“cure”). Second, some results also suggested a delayed effect - observed as late separation of survival curves between experimental and control arms. Both long-term survival and delayed onset of benefit may be linked to the mechanisms of action of I-O drugs. As these phenomena are expected to be observed in the current disease setting as well, a piecewise mixture cure rate model was used for the design setup.

Sample size calculations assume that the prevalence of subjects with PD-L1 tumor expression level  $\geq 1\%$  is approximately 50%. (During enrollment, the proportion of subjects with or without PD-L1 tumor expression will be monitored, and may be re-assessed in case it does not reflect study assumptions.)

In addition, proportion of patients in the chemotherapy arm who receive I-O as subsequent therapy will be monitored; protocol may be amended accordingly.

**The sample size is based on the primary objectives, ie, on the comparisons of the PFS/OS distributions of subjects with PD-L1 expressing tumors** between those who were randomized to receive nivolumab plus ipilimumab vs those randomized to receive chemotherapy, and between those who were randomized to receive nivolumab plus chemotherapy vs those randomized to receive chemotherapy.

For both experimental arms, the same OS distributions and the same PFS distributions are assumed (see [Table 8.1-1](#)). As a result, for each of the nivolumab plus ipilimumab vs chemotherapy and nivolumab plus chemotherapy vs chemotherapy comparisons:

- 250 PFS events in approximately 313 subjects with PD-L1 expressing tumors will provide approximately 90% power to detect an average HR of 0.62 with a Type I error of 1.5% (two-sided);
- 250 OS events in approximately 313 subjects with PD-L1 expressing tumors will provide approximately 90% power to detect an average HR of 0.6 with a Type I error of 1% (two-sided).

To have approximately 313 randomized subjects with PD-L1 expressing tumors for each comparison, approximately 470 subjects with PD-L1 expressing tumors need to be randomized in in a 1:1:1 ratio in the 3 arms. Which therefore translates to a total of approximately 939 subjects (with any PD-L1 result) to be randomized in a 1:1:1 ratio to the nivolumab plus ipilimumab or nivolumab plus chemotherapy or chemotherapy arms. Assuming a piecewise constant accrual rate, it is estimated that these 939 subjects will be accrued within 29 months.

Although for the comparison of both experimental arms with the control arm, the same treatment effect is assumed, observed treatment effects may vary. Therefore, the events of interest (OS, PFS) observed in the chemotherapy arm *only* will be used for determining the timing of the interim and final efficacy analyses. Final PFS analysis is planned when 136 PFS events per BICR are observed among the PD-L1 expressing subjects in the chemotherapy arm. This is expected to be reached after approximately 33 months. If the planned number of PFS events is unlikely to be reached for any unforeseen reasons, the final PFS analysis may occur when at least 12 months minimum follow-up (defined as the time from the date when the last patient was randomized to the clinical cutoff date) is reached. Should this scenario occur, corresponding to PFS events of 110 and 121, the power would be 80% and 85%, respectively (details of this scenario are discussed in Appendix 7 of the SAP). Final OS analysis is planned when 140 events are observed among the PD-L1 expressing subjects in the chemotherapy arm. This is expected to be reached after approximately 49 months. (At the time of the final PFS analysis, a formal interim analysis for OS will be conducted, see [Section 8.5.](#))

Details of the sample size calculations for the subjects whose tumors express PD-L1 are provided in Table 8.1-1.

Table 8.1-1: Subjects whose Tumors Express PD-L1 - Summary of Sample Size Parameters and Schedule of Analyses (Nivolumab plus Ipilimumab vs Chemotherapy and Nivolumab plus Chemotherapy vs Chemotherapy)		
	OS	PFS
# of randomized subjects	≈313 (total in the 3 arms: ≈470)	
Hypothesized delayed effect	3 months	1 month
Hypothesized cure rate in experimental arms	15%	0
Hypothesized HR after delayed effect, in non-cure subjects	0.65	0.55
Hypothesized median: control vs experimental	9 months* vs 14.4 months	4 months vs 6.4 months
Significance level	0.01	0.015
FINAL ANALYSIS		
Criteria for time of LPLV	140 events are observed among the PD-L1 expressing subjects in the chemotherapy arm	136 events are observed among the PD-L1 expressing subjects in the chemotherapy arm
Projected time of LPLV (from randomization)	49 months	33 months
Projected # of events	250	250
Significance level	[0.009] a	0.015
Power	90%	90%

Table 8.1-1: Subjects whose Tumors Express PD-L1 - Summary of Sample Size Parameters and Schedule of Analyses (Nivolumab plus Ipilimumab vs Chemotherapy and Nivolumab plus Chemotherapy vs Chemotherapy)		
	OS	PFS
Hypothesized overall HR	0.6	0.62
Critical HR (b) / Minimal difference in median (c)	0.72 / 3.5 months	0.73 / 1.4 months
INTERIM ANALYSIS for OS		
Criteria for time of LPLV	At the time of PFS final analysis	N/A
Projected # of events	≈175 (70% of all events)	N/A
Significance level	[0.002] (a)	N/A
Probability of crossing boundary	29%	N/A
Hypothesized overall HR	0.67	N/A
Critical HR b / Minimal difference in median c	0.62 / 5.6 months	N/A

a For OS, significance levels will be recalculated based on the actual number of deaths at interim analysis

b Largest observed HR at which a statistically significant difference would be observed

c Difference in median, corresponding to a minimal clinically significant effect size

\* Asia: 10 months, RoW: 6 months

Analyses on OS and PFS in all randomized subjects will be carried out at the time of the primary analysis (in subjects whose tumors express PD-L1); OS and PFS in all randomized subjects are expected to be mature by that time. They will be tested only if significance level is passed on them. Details of the related power calculations are provided in Table 8.1-2.

Table 8.1-2: All Randomized Subjects - Summary of Power Calculation Parameters and Schedule of Analyses (Nivolumab plus Ipilimumab vs Chemotherapy and Nivolumab plus Chemotherapy vs Chemotherapy)		
	OS	PFS
# of randomized subjects	626 (total in the 3 arms: 939)	
Hypothesized delayed effect	3 months in PD-L1+, 4 months in PD-L1-	1 month in PD-L1+, 2 months in PD-L1-
Hypothesized cure rate in experimental arms	15% in PD-L1+, 10% in PD-L1-	0

Table 8.1-2: All Randomized Subjects - Summary of Power Calculation Parameters and Schedule of Analyses (Nivolumab plus Ipilimumab vs Chemotherapy and Nivolumab plus Chemotherapy vs Chemotherapy)		
	OS	PFS
Hypothesized HR after delayed effect, in non-cure subjects	0.65 in PD-L1+, 0.85 in PD-L1-	0.55 in PD-L1+, 0.75 in PD-L1-
Hypothesized median: control vs experimental	9 months* vs 12.3 months	4 months vs 5.5 months
Significance level a	0.01	0.015
FINAL ANALYSIS		
Criteria for time of LPLV	At the time of the PD-L1+ LPLV	At the time of the PD-L1+ LPLV
Projected # of events	≈514	≈512
Significance level a	[0.009] b	0.015
Power c	94%	90%
Hypothesized overall HR	0.68	0.72
Critical HR d / Minimal difference in median e	0.80 / 2.3 months	0.81 / 0.9 months
INTERIM ANALYSIS for OS		
Criteria for time of LPLV	At the time of PFS final analysis	N/A
Projected # of events	≈362 (70.4% of all events)	N/A
Significance level a	[0.002] (a)	N/A
Probability of crossing boundary c	33%	N/A
Hypothesized overall HR	0.75	N/A
Critical HR b / Minimal difference in median e	0.74 / 3.1 months	N/A
Accrual rate per month	Gradually increasing accrual rates (max = 45 subjects per months)	
Accrual Duration	29 months	

a In case the significance level from the corresponding primary endpoint is passed. (Note that endpoint-specific [i.e. initially allocated] significance level is 0.)

b For OS, significance levels will be recalculated based on the actual number of deaths at interim analysis

c Not accounting for hierarchy

d Largest observed HR at which a statistically significant difference would be observed

e Difference in median, corresponding to a minimal clinically significant effect size

\* Asia: 10 months, RoW: 6 months

Simulations were conducted in R-v3.1.3.

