Per protocol, the planned interim analysis (PFS final analysis and OS interim analysis) will be triggered when 136 PFS events per blinded independent central reviewer (BICR) are observed among subjects expressing at least 1% tumor PD-L1 in the chemotherapy arm (Arm C). PFS event tracking is conducted by an independent external statistical group (Axio, Inc), which supports statistical analyses and generates reports for review by an independent Data Monitoring Committee. BMS remains blinded to the number of PFS events in arm A and arm B. Event tracking commenced in July 2020. PFS events are observed to be tracking at a much slower rate than projected per protocol. This is largely due to censoring due to start of subsequent therapy or withdrawal of consent prior to progression, the extent of which was unforeseen when this protocol was developed.

This protocol amendment adds another trigger for the interim analysis (Final PFS/Interim OS) in the event that the target number of PFS events is not reached. The revised protocol allows for the final PFS analysis to be triggered when 136 PFS events are observed among the PD-L1 expressing subjects in the chemotherapy arm, or when at least 12 months minimum follow up (defined as the time from the date of the last patient was randomized to the clinical cutoff date) is reached. In the eventuality that the target number of PFS events is not reached, the 12 months minimum follow-up ensures adequate follow-up for PFS in this patient population.

As per original design, OS IA will be conducted at the same time as PFS final analysis (FA) and the alpha allocation will be calculated per the specified method (see section 7.5 of SAP).

SUMMARY OF KEY CHANGES FOR REVISED PROTOCOL 05		
Section Number & Title	Description of Change	Brief Rationale
Synopsis, Section 8.1: Sample Size Determination	Amended trigger for the IA	Added provision for triggering the planned IA when at least 12 months minimum follow-up is reached, in the eventuality that the planned 136 PFS events per BICR among the PD L1 expressing subjects in the chemotherapy are unlikely to be reached.

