#### APPENDIX 7 CHANGE OF THE TRIGGER FOR PFS FA/OS IA

Per the original protocol, the planned interim analysis (PFS final analysis and OS interim analysis) was to be triggered when 136 PFS events per blinded independent central review committee (BICR) are observed among the PD-L1 expressing subjects in the chemotherapy arm (Arm C). The primary PFS endpoint is based on the primary PFS definition (i.e. PFS events truncated at subsequent therapy as defined in Section 8.3.1). PFS event tracking is conducted by an independent external statistical group (Axio, Inc) which supports statistical analyses and generates reports for review by an independent Data Monitoring Committee. Event tracking commenced in July 2020 and per tracking plan, BMS has been receiving information on the number of PFS events per primary and secondary (PFS events not truncated by subsequent therapy, sensitivity analysis in Section 7.5.2.2) definitions. BMS remains blinded to the number of PFS events in the experimental arms.

Based on the latest event tracking report (report is stored in eTMF Section 01.03.03 Committee report) utilizing the September 16 2020 BICR data transfer (data is stored in unix folder "/gbs/prod/clin/data/ca/209/648/stable/blinded/level2"), a total of 102 PFS events per BICR were observed by primary definition among the PD-L1 expressing subjects in Arm C. The PFS events per secondary definition was 135 among the PD-L1 expressing subjects in Arm C and upon further investigation, it could be determined that the target of 136 PFS events per BICR for triggering the interim analysis (IA) per protocol is unlikely to be reached for the reasons specified below, acknowledging that data review is ongoing.

- Under the 1:1:1 randomization ratio and based on the assumption of 50% (from Protocol Section 3.1) and 48.3% (% of patients in the control arm in Table 11.2-1 in the ONO-4538-24 (CA209473) Primary Clinical Study Report (CSR)) for prevalence of Tumor PD-L1 expression ≥ 1% in advanced ESCC, it is estimated that approximately 158 PD-L1 expressing subjects would be randomized to the chemotherapy arm.

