- Assuming 158 PD-L1 expressing subjects randomized to the chemotherapy arm and considering the number of 102 PFS events observed so far, there would be an additional 158-102=56 subjects for whom a PFS event may still be expected per primary definition. However, per secondary definition which accounts for disease progression after subsequent therapy, a total of 135 PFS events per BICR were observed. Therefore, it is evident that for 135-102=33 subjects, PFS events per primary definition should not be expected.
- Event tracking in all randomized subjects across the three treatment arms indicated there are a total of 94 subjects are censored per primary definition due to withdrawal of consent, lost to follow-up, no scans or without PD/death after subsequent therapies. Assuming equal subject distribution across treatment arms and PD-L1 expression subgroups, it is estimated that 15 of these subjects would represent PD-L1 expressing subjects in the chemotherapy arm, thus reducing the potential pool of subjects for whom a PFS event could be expected even further.
- Therefore, among the 56 subjects without observed PFS events (per primary definition), only 56-33-15=8 subjects may contribute a PFS event per primary definition, whereas an additional 34 PFS events are needed to trigger the IA.

Based on the reasons stated above, the IA will be performed when 136 PFS events are observed or when a 12-month minimum follow-up (defined as the time from the date the last patient was randomized to the clinical cutoff date) is reached if the target number of events is unlikely to be reached among the PD-L1 expressing subjects in the chemotherapy arm. The table below provides the power based on different numbers of PFS events among PD-L1+ subjects in chemo arm using the same protocol assumption.

	Total number of PFS events for one	
PFS events among PD-	comparison (i.e. for N+I vs CT; and	
L1+ in chemo	for N+C vs CT)	Power
136	250	90%
121	218	85%
110	195	80%
100	175	75%

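### The OS interim projections describe a look near month 33 and were not restated for the 12-month follow-up fallback; the all-randomized rows also use the wrong spending function

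*Protocol*

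**What the plan says.** **Timing.** The Revised Protocol 05 rationale states that "OS IA will be conducted at the same time as PFS final analysis (FA"). Protocol 8.1 expects that analysis at about month 33, when 136 control-arm PFS events have been seen. If that count is unlikely to be reached, "the final PFS analysis may occur when at least 12 months minimum follow-up" after the last randomization has accrued.

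**Which path is expected.** SAP Appendix 7 says "the target of 136 PFS events per BICR for triggering the interim analysis (IA) per protocol is unlikely to be reached". It counts 102 events so far and concludes that "only 56-33-15=8 subjects may contribute a PFS event per primary definition, whereas an additional 34 PFS events are needed to trigger the IA". That is about 102 + 8 = 110 events against 136.

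**What was restated.** For the fallback, Protocol 8.1 gives PFS power only: "corresponding to PFS events of 110 and 121, the power would be 80% and 85%, respectively". SAP section 5 and the Appendix 7 table do the same.

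**What was not.**
- Protocol Table 8.1-1 and SAP Table 5-1 (PD-L1 expressing): projected deaths "175 (70% of all events"), level 0.002, overall HR 0.67, critical HR 0.62, minimal median difference 5.6 months, 29% crossing.
- Protocol Table 8.1-2 and SAP Table 5-2 (all randomized): "362 (70.4% of all events"), level 0.002, overall HR 0.75, critical HR 0.74, 33% crossing.

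SAP version 4.0, issued after the amendment, keeps these rows. A footnote says: "For OS, significance levels will be recalculated based on the actual number of deaths at interim analysis". SAP 7.5.1 assigns O'Brien-Fleming spending to primary OS and Pocock spending to OS in all randomized subjects.

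**The concern.** PFS events fell short largely because subjects are censored at subsequent therapy or withdraw consent. OS is not censored at subsequent therapy, so deaths keep accruing while PFS stalls. A look moved from month 33 to month 41 or later therefore sees many more deaths, and the printed OS rows no longer describe it.

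OS in PD-L1 expressing subjects is a primary endpoint, the DMC makes recommendations at this look, and SAP section 1 says the study may be stopped on a significant result. The tables present an early look that, per comparison, is expected not to cross (71%). On the fallback path and the same design assumptions, crossing becomes the likelier result. A reader of the tables would not learn this.

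The all-randomized rows raise a second question that does not depend on the fallback: their level of 0.002 does not match the spending function that the SAP names for that endpoint.

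**Working it through.** **Inputs.** From the SAP Appendix 6 program: 626 subjects per comparison, its 29-month accrual vector, 80% Asia and 20% West, half PD-L1 expressing. OS delay is 3 months (PD-L1 expressing) or 4 months (non-expressing); cure is 15% or 10%; HR after the delay is 0.65 or 0.85. Control medians of 10 months (Asia) and 6 months (RoW) are from the table footnote. Final deaths are 250 (PD-L1 expressing) and 514 (all randomized). The program has no dropout. I re-coded it with a calendar cutoff and a Cox Wald test, in 4,000 to 6,000 runs per scenario.

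**Formulas** (d deaths out of D, t = d/D, overall two-sided alpha 0.01):
- O'Brien-Fleming level = 4 × [1 − Φ(2.807/√t)]
- Pocock level = 0.01 × ln(1 + 1.718t)
- critical HR = exp(−2z/√d), with z the two-sided normal quantile of the level
- minimal median difference = 9 × (1/critical HR − 1)

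**1. The plan's own figures reproduce.** Taking the look at exactly 175 deaths, t = 0.70:
- median time is month 32.7
- level 4 × [1 − Φ(3.355)] = 0.0016, which rounds to 0.002
- critical HR exp(−2 × 3.158/√175) = 0.62
- crossing 28.2% (stated 29%)
- final power 90.7% (stated 90%)

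A calendar cut at month 33 gives 177 deaths and about 29%.

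**2. Fallback, PD-L1 expressing, per comparison.** The earliest date on planned accrual is 29 + 12 = month 41.

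| Assumed annual loss | Deaths | t | Level | Critical HR | Median difference (months) | Crossing |
|---|---|---|---|---|---|---|
| 0% | 222 | 0.888 | 0.0058 | 0.69 | 4.0 | 75% |
| 5% | 215 | 0.860 | 0.0049 | 0.68 | 4.2 | 70% |
| 10% | 207 | 0.828 | 0.0041 | 0.67 | 4.4 | 63% |

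For the first row: 4 × [1 − Φ(2.979)] = 0.0058; exp(−2 × 2.76/√222) = 0.69; 9 × (1/0.69 − 1) = 4.0. The overall HR with no loss is about 0.63, against 0.67 in the tables.

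**3. Sensitivity to dates (no loss).**
- Accrual rescaled to 24 months: 216 deaths, 69%.
- Accrual rescaled to 34 months: 227 deaths, 80%.
- Planned accrual, cutoff at month 44: 234 deaths, 84%.

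**4. Overall power.** With the final at month 49 and no loss:
- interim at month 33: 28.7% cross then, 91.6% overall; the interim share is 28.7/91.6 = 31%
- interim at month 41: 74.9% cross then, 90.9% overall; the interim share is 74.9/90.9 = 82%

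Overall power barely moves.

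**5. All randomized subjects** (not accounting for hierarchy, as in the tables). O'Brien-Fleming at t = 0.704 gives 0.0016 and about 32% crossing, which matches the stated 0.002 and 33%. So the rows were built on O'Brien-Fleming. Under the Pocock spending in SAP 7.5.1:
- interim level 0.01 × ln(1 + 1.718 × 0.704) = 0.0079
- crossing about 53% at month 33
- final level about 0.004, against the printed 0.009
- critical HR by formula exp(−2 × 2.655/√362) = 0.76 at interim and exp(−2 × 2.871/√514) = 0.78 at final (printed 0.74 and 0.80)

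At month 41 with no loss there are 460 deaths (t = 0.894), a level of 0.0093 and 85% crossing; with 10% loss, 77%.

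**The case against.** **Nothing operational is wrong.** The 175-death, 0.002 figures are framed as an example in Protocol 8.5 and as a conditional case in SAP 7.5.1. The table levels are bracketed and footnoted as recalculated, and SAP 7.5.1 computes the level from actual pooled deaths. Nobody following the plan would apply 0.002 at 222 deaths. This stands. A reader might infer that the stale rows inflate Type I error or set a wrong boundary; the documents do not support that.

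**The tables record the original design.** Their PFS rows also still show 250 events, 33 months and 90% power, so the OS rows were not singled out within the tables. This stands too, and it argues for putting the new figures in Appendix 7 beside the PFS ones. It does not remove the gap, because no fallback OS figure appears anywhere.

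**75% is the no-loss figure.** Withdrawal of consent is part of the reason for the amendment, so some loss is plausible, and the documents give neither the OS loss rate nor the last-randomization date. Subsequent immunotherapy in the control arm, which Protocol 8.1 says will be monitored, is not modelled. The range must be shown.

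**The figures are per comparison at the initial alpha.** Two comparisons share a control. If PFS is rejected in both populations, OS alpha rises to 0.0175, and month-41 crossing with no loss to about 80%. Reading 63% to 75% as the chance that the trial succeeds at the interim would therefore be wrong.

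**No wrong stopping decision follows.** A stop at 83% to 89% information would rest on more mature OS data than the planned 70% look. A reader might infer a risk of premature stopping; the documents do not support it.

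**Conclusion.** The point holds as a stale stated projection, not as a decision error. The OS interim rows describe a look near month 33, while the amended plan expects one at 12 or more months after last randomization. On the design's own OS assumptions, per comparison at alpha 0.01, with planned 29-month accrual and a month-41 cutoff, the PD-L1 expressing interim would have about 207 to 222 deaths (83% to 89% information) and 63% to 75% crossing, against 175 and 29% in the tables. The ends of the range are assumed annual losses of 10% and 0%. Every accrual, cutoff and loss scenario checked gives more than twice the stated 29%. Confidence is high in the omission and in the direction, lower in any single percentage.

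The mismatch in the all-randomized rows is a separate error that holds on any path: 0.002 and 33% should be about 0.008 and 53% at month 33 under the spending function that the SAP specifies.

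**What to change.** 1. In SAP Appendix 7, beside the PFS power table, add fallback OS interim rows for both populations: projected deaths, information fraction, level, overall HR, critical HR, minimal median difference and crossing probability. Rerun the Appendix 6 program with a calendar cutoff, the actual accrual dates and a stated loss assumption (for example 0%, 5% and 10% per year). State the alpha used and that the figures are per comparison. Cross-reference the rows from Protocol 8.1, Protocol Tables 8.1-1 and 8.1-2, and SAP Tables 5-1 and 5-2.
2. In Protocol Table 8.1-2 and SAP Table 5-2, correct the all-randomized OS interim and final levels, critical HRs and crossing probability to the Pocock spending in SAP 7.5.1. The 94% final power was simulated at the O'Brien-Fleming final level, so rerun it at the same time.

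The cost is a rerun of existing code with two added parameters, plus table and text edits. Tests, alpha, sample size, triggers and conduct do not change.
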